9.3 RADIATION THERAPY

External beam radiation therapy will be applied to a minimum of one or more selected lesions in 5 daily fractions, over five to eight days, at a dose of 20Gy.

The number of lesions to be irradiated will be at the discretion of the investigator as clinically indicated. Lesions which directly receive radiotherapy will be categorized as “irradiated lesions” with all other lesions identified as “non-irradiated lesions”.

Lesions will be assessed by the investigational site at screening and any symptomatic lesion/s for irradiation which can be assessed by RECIST 1.1 criteria will be noted as “measurable irradiated target lesions” and symptomatic lesions that cannot be measured will be noted as “non-measurable lesions”. Further detail is provided in Section 10.4.8. Lesions will be captured by CT or MRI scan at baseline with follow-up CT/MRI imaging at Week 6, Week 12 and Week 24. Scan image data will be stored on central planning system software (such as *MIM*) for radiological comparisons and response to treatment will be reported.

During screening period, baseline lesion/s will be selected for irradiation and the gross tumour volume (GTV), the clinical target volume (CTV) and organs at risk (OAR) will be defined by the radiation oncologist based ICRU 50 or ICRU 83 guidelines.

Radiation therapy will be delivered to target labelled irradiation lesions according to the study radiation treatment plan developed. Details are provided in the NOX66-002A **Radiation Therapy Planning, Delivery and QA Guidelines** which must be used as the primary source for planning and delivering radiation therapy treatment within the trial.

Tumour lesions either for irradiation or not which, at baseline, are identified as measurable will be noted as target lesions and will be assessed for response to treatment according to RECIST 1.1 criteria. Symptomatic tumour lesion which at baseline is identified for irradiation but not measurable will be noted a non-measurable target lesion/s.

All radiological scans during the study will be reviewed by the independent Radiation Oncology Expert Committee for each patient to assess overall response to treatment.

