5.1.2 Abscopal Response

An abscopal (from Latin ab-scopus, away from the target) response describes tumour regression at sites distant to an irradiated field, and is a rare event seen in patients with various types of metastatic tumours receiving palliative radiation therapy to a single metastasis. First described²⁹ over 50 years ago, the response is sufficiently rare to warrant clinical reports of individual cases, with responses in melanoma, lung cancer, kidney cancer and cutaneous lymphomas variously reported.³⁰⁻³³

In the only prospective clinical study³⁴ reported to date, 41 patients with metastatic solid cancers were treated with a combination of standard cytotoxic chemotherapy, external beam RT, and granulocyte-macrophage colony stimulating factor (GM-CSF). A maximum 2 lesions were irradiated (35 Gy in 10 fractionated doses) and the response measured by CT scan in both irradiated and non-irradiated lesions. An abscopal response was reported in 11/41 (27%) patients (4 lung cancer, 5 breast cancer, 2 thymic cancer). Two of these cases had a complete response (lung cancer) and 9 had a partial response. The median overall survival was 21 months for abscopal responders versus 8 months for the non-responders.

While the mechanism underlying this phenomenon is unknown, the results of the above study, in conjunction with a range of pre-clinical studies, points to the involvement of soluble signalling factors including tumour antigens that are hypothesized to be released by the dying irradiated tumour cells to mediate an immune response against non-irradiated lesions.^{35,36,37}

In addition to its anti-cancer effects, idronoxil also has confirmed immune-stimulatory effects.³⁸ Human peripheral blood CD56+ natural killer (NK) cells show increased lytic activity against K562 (myelogenous leukaemia cell line) in the presence of idronoxil. Also, in a mouse colon cancer (CT-26) model in which idronoxil monotherapy produced a significant anti-cancer effect, ex vivo studies showed that idronoxil activated both NK and tumour-specific tumour cell lysis. As such, it is hypothesized that NOX66 may produce an abscopal effect in treating non-irradiated lesions when combined with radiation therapy.

In this study, we will also monitor for any changes in non-irradiated lesions, to determine if NOX66 may induce an abscopal response when combined with radiation therapy.

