7 STUDY DESIGN

This is an open-label Phase Ib dose confirmation and proof of concept study in up to 24 patients with end stage castrate resistant prostate cancer who are being considered for or undergoing palliative radiation therapy for pain and symptom management. Patients will have a minimum of one (1) lesion which is amenable to radiation therapy. Palliative RT (20Gy over 5 fractions) will be delivered to selected lesion in combination with rectally administered idronoxil (NOX66).

This study is intended to provide information regarding the safety of this treatment combination and justification for a larger Phase 2/3 study in the treatment of patients with combination of NOX66 and palliative radiation therapy.

Clinical response to treatment will be assessed by radiological CT/MRI scans, where applicable objectively measures by RECISTv1.1, by pain response as evaluated by Brief Pain Inventory Short Form, ECOG scores and by monitoring PSA as surrogate marker with overall (observable and symptomatic) response based on data review by an independent Radiation Oncology Expert Committee (ROEC). Local response will be based on investigator review of data in conjunction with ROEC.

PSA will be monitored as a surrogate marker of response and pain response will be evaluated using the Brief Pain Inventory Short Form throughout the study.

Patients will be suitable for the study as they become eligible for, and will be given, palliative radiation therapy for management of their cancer.

Three dose cohorts will be investigated in this study with dosing based on criteria outlined in section 10.2.7. The three doses of idronoxil investigated include:

- 400mg idronoxil provided as one NOX66 suppository per day
- 800mg idronoxil provided as one NOX66 suppository twice daily
- 1200mg idronoxil provided as one NOX66 suppository three times daily.

Treatment will be for one cycle of combined radiation therapy and NOX66 with follow up assessments at Week 6, Week 12, Week 24 and every 3 months for the following 18 months. All patients will be followed up for disease progression and survival information either by retrospective review of medical records or by a physical visit or by telephone follow up call.

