8.2 INCLUSION CRITERIA

Patients must fulfil all of the following inclusion criteria to be eligible to enrol into the study:

1. Provision of informed consent.
2. ≥ 18 years of age.
3. Histologically confirmed prostate cancer and/or PSA of > 100 ng/mL at original diagnosis
4. Metastatic disease evidenced by either CT/MRI imaging or bone scan.
5. Objective evidence of disease progression as defined by either:
 - i. Radiographic progression of in nodal or visceral metastases and bone disease progression with 2 or more new lesions
 - ii. Rising PSA value ≥ 2 ng/ml in at least 3 measurements, at least 1 week apart, with castrate levels of serum testosterone.
6. Eligible to receive palliative radiation therapy to at least one symptomatic lesion for management of disease.
7. ECOG Performance status 0-2.
8. A minimum life expectancy of 24 weeks.
9. Adequate bone marrow, hepatic and renal function as evidenced by:
 - Absolute neutrophil count (ANC) $> 1.5 \times 10^9$ /L
 - Platelet count $> 100 \times 10^9$ /L
 - Hemoglobin > 9.0 g/dL
 - Serum bilirubin $< 1.5 \times$ ULN
 - AST/ALT (SGOT/SGPT) $< 2.5 \times$ ULN for the reference laboratory or $< 5 \times$ ULN in the presence of liver metastases
 - Serum creatinine $< 1.5 \times$ ULN
10. Ongoing androgen deprivation therapy with luteinizing hormone-releasing hormone (LHRH) agonist or antagonist.
11. At least 4 weeks must have elapsed prior to commencement of NOX66 treatment since prior chemotherapy, investigational drug or biologic therapy and any toxicity associated with these treatments has recovered to \leq NCI-CTCAE (version 4.03) Grade 1.
12. At least 21 days must have elapsed following major surgery and any surgical incision should be completely healed.

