10.2.1 Screening Visit (VS)

The purpose and the procedures of the Study will be fully explained to participants at the screening visit and every patient approached regarding the study will be provided with the Informed Consent Form (ICF). Patients wishing to enrol in the Study will sign the ICF prior to initiating any study related investigations or procedures.

All screened patients who sign the ICF must be recorded on the Screening/Enrolment Log. If a patient who signs an ICF is not enrolled in the study, the reason will be noted. The Screening/Enrolment Log will be retained within the Investigator Site File.

The following procedures are to be performed at the screening visit to occur within 2 weeks of commencement of NOX66 treatment:

- Obtain Informed Consent
- Review and confirm eligibility (Inclusion / Exclusion Criteria)
- Medical History and Demography, including review of any prior radiation therapy and toxicities / adverse events
- Physical Examination including vital signs
- Performance Status Assessment (using ECOG performance scale)
- Safety blood sampling – Complete Blood Count, Serum Chemistry, and Urinalysis; and results within 5 days of enrolment
- Blood sample for serum PSA and testosterone
- Electrocardiography (12-lead) in triplicate
- Concomitant Medication Review
- Tumour Imaging (CT/MRI) including measures of target lesions- baseline
- Administration of Brief Pain Inventory -Short Form questionnaire

Radiological scans performed prior to consent may be utilized for the purposes of the study if they have been performed as part of routine clinical practice and the patient consents for their medical records to be reviewed by the Sponsor, the scans were performed in the 28 days prior to the screening visit (i.e. they can be considered current evidence of tumour size) and they can provide suitable tumour measurements and assessments of target and non-target lesions.

The Principal Investigator will maintain a confidential log of all patients who have been screened for participation in the study whether or not the patient was eligible for study participation

10.2.2 Enrolment Visit (V1):

Once eligibility is confirmed patients will be contacted to attend clinic for:

- education on self-administration and dispensing of NOX66 for use from Day 1 of the treatment cycle
- baseline biomarker blood sample for idronoxil

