10.4.8 Tumour Imaging

Tumour imaging by CT/MRI will be performed in line with local practices using a planning software system.

Baseline documentation of Target and Non-Target lesions

'Target' lesions are assessed at the designated scanning time points and defined as lesions that are measurable and:

Irradiated, such as soft tissue and lytic bony lesions, have defined margins for measurement and are irradiated at the discretion of the investigator. These lesions will be noted as 'irradiated measurable target'.

- Non-irradiated and these lesions will be noted as 'non-irradiated measurable target'.

For measurable lesions, the Longest Diameter (LD) of each lesion will be measured and a sum of the LD will be calculated and reported as the baseline sum LD. The sum LD will be used as reference by which to characterize the objective tumour response based on RECIST v1.1 criteria (see below).

Patients will undergo baseline CT or MRI body scan. A maximum of 5 lesions in total, with no more than 2 lesions per organ, will be identified as target lesions.

'Non-Target' lesions include all other lesions and are recorded at baseline as either measurable or non-measurable. For non-measurable lesions, the presence or absence of each will be noted throughout follow-up scanning time points. For measurable lesions, size (mm) will be noted throughout follow-up scanning time points.

These can include irradiated lesions such as sclerotic bone lesions, which do not have defined margins for measurements and are irradiated at the discretion of the investigator. These lesions will be assessed for local response based on patient reported outcome using the BPI-SF (see section 10.4.5).

Review of all CT/MRI scans per patient will be conducted by the independent Radiation Oncology Expert Committee as outlined in Section 10.4.9.

RECIST evaluation of target lesions

Assessment of irradiated measurable lesions will be conducted according to the RECIST1.1 Criteria for response on the CT or MRI scan, as set out below.

Complete Response (CR):	Disappearance of all relevant target lesions
Partial Response (PR):	At least a 30% decrease in the sum of the LD of relevant target lesions, taking as reference the baseline sum LD
Stable Disease (SD):	Neither sufficient shrinkage to qualify for PR nor sufficient increase to qualify for PD, taking as reference the smallest sum LD since the treatment started

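### A lesion irradiated before the study falls by default into the 'non-irradiated' class, so late shrinkage from earlier radiotherapy can be read as an abscopal effect

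*Combined protocol and SAP*

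**What the plan says.** Section 9.3 sorts lesions in one sentence: "Lesions which directly receive radiotherapy will be categorized as “irradiated lesions” with all other lesions identified as “non-irradiated lesions". The second half, "with all other lesions identified as “non-irradiated lesions", leaves no third class. The same section makes target status depend on measurability: "Tumour lesions either for irradiation or not which, at baseline, are identified as measurable will be noted as target lesions". Section 10.4.8 repeats this for the second class: "Non-irradiated and these lesions will be noted as 'non-irradiated measurable target". Its other limits on target lesions are five in total and two per organ.

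Prior radiotherapy appears once in the study procedures, within the medical history taken at screening (section 10.2.1): "including review of any prior radiation therapy and toxicities / adverse events". In section 8.2, criterion 11 sets an interval for other treatments: "At least 4 weeks must have elapsed prior to commencement of NOX66 treatment since prior chemotherapy, investigational drug or biologic therapy". Radiotherapy is not on that list.

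The class matters because section 5.1.2 says "we will also monitor for any changes in non-irradiated lesions, to determine if NOX66 may induce an abscopal response". Section 10.1 lists change in size of non-irradiated target lesions as a secondary outcome, and hypothesis (c) in section 4 concerns an effect on non-irradiated tumours.

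**The concern.** An abscopal response is shrinkage of a tumour that radiation did not reach. The comparison is sound only if the lesions called non-irradiated really had none. Under a two-class rule keyed to study treatment, a node irradiated shortly before enrolment, and still shrinking, would sit among the lesions meant to show an indirect effect.

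The study has no randomisation (section 8.1) and no control arm, so nothing in the design would reveal the carry-over. Section 5.1.2 calls abscopal responses rare, so even an isolated false one would attract attention. Week 6 RECIST signals from the first 12 patients also inform the dose chosen for the expansion cohort (sections 10.2.14 and 13.2).

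**Working it through.** The plan gives no figure on this point to reproduce. The sample size is a cohort sum (3 × 4 + 12 = 24) with no error rate, power or effect size behind it. The check is therefore a reading of the rules, followed by simple arithmetic.

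**1. Which class does a previously irradiated lesion enter?** Section 9.3 describes study radiotherapy, and lesions are labelled at screening according to whether they are to be irradiated. In that setting the first class means lesions given study radiotherapy. A lesion treated earlier and not selected now belongs with all the others.

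**2. Does another rule remove it?**
- Section 8.2, criterion 11: chemotherapy, investigational drugs and biologics only.
- Section 8.2, criterion 12: major surgery only.
- Section 8.3, exclusion 4: concurrent systemic chemotherapy or biological therapy only. Exclusion 8 is investigator discretion.
- Section 8.2, criterion 5(ii): a PSA rise suffices for progression, so the earlier-treated lesion need not have regrown.
- Section 10.2.1: prior radiotherapy is reviewed, but the review is tied to no rule on lesion class or target selection.
- Section 12.2: the efficacy population depends on completing radiotherapy with at least 7 days of NOX66, not on lesion history.

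None of these removes it.

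**3. Is carry-over possible in time?** A routine scan may precede the screening visit by 28 days (section 10.2.1), and screening may precede treatment by 14 days (section 10.2).
- Baseline scan to Day 1: 28 + 14 = 42 days.
- Day 1 to the latest Week 6 scan, Day 43 + 5 = Day 48: 47 days.
- Longest gap from baseline scan to first response scan: 42 + 47 = 89 days.

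Radiotherapy given shortly before the baseline scan, or between that scan and Day 1, could produce shrinkage measured from that baseline.

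**4. What can one lesion do?** Section 10.4.8 requires a fall of at least 30% in the sum of longest diameters of the relevant targets. Assume the sum is taken over non-irradiated targets and the other lesions do not change. If the earlier-treated lesion makes up a share w of the baseline sum and shrinks by a fraction s, the sum falls by w × s, and a partial response needs w × s ≥ 0.30.
- Only non-irradiated target (w = 1): s ≥ 30%.
- One of two equal targets (w = 1/2): s ≥ 60%.
- One of three equal targets (w = 1/3): s ≥ 90%.
- One of four or five equal targets: complete disappearance gives only 25% or 20%, so no partial response.

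**5. Scale, by assumption.** The documents give neither the share p of patients with such a target lesion nor the fraction r of those whose earlier radiotherapy produces a qualifying fall. The chance of at least one false response among n patients is 1 − (1 − p × r)^n. I assume p from 10% to 50% and r from 10% to 30%.
- n = 12: from 1 − 0.99^12 = 11% to 1 − 0.85^12 = 86%.
- n = 24: from 1 − 0.99^24 = 21% to 1 − 0.85^24 = 98%.

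The width of these ranges shows that the documents do not determine the size.

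**The case against.** **The wording is open.** The first half of the sentence in section 9.3 is not expressly limited to study radiotherapy, and no sentence says that a previously irradiated lesion is non-irradiated. That is fair: the classification follows from a two-class rule read in context. The other reading would put the lesion among the irradiated ones, mixing earlier with study radiotherapy, so clarification is needed either way.

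**Other documents may cover it.** Measurability is delegated to RECIST 1.1, and a separate radiotherapy guideline is cited. Neither can be checked here. Section 9.3 cites the guideline for planning and delivery, not for classifying response. If the sponsor relies on either for this purpose, the protocol should say so.

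**Independent experts review the scans.** The committee in section 10.4.9 receives scans, PSA, ECOG and pain scores. Radiotherapy history is not among its listed inputs, and it has no stated rule for such lesions. This is partial protection.

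**The effect may be small.** Section 12.1 itself expects less than a 30% reduction from palliative radiotherapy alone, and the outcome is secondary and descriptive. This limits the chance of a false partial response. It does not remove the problem: earlier radiotherapy need not have been palliative, and section 5.1.2 looks for any change, not only partial responses.

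**Safety.** A reader might infer that ongoing toxicity from earlier radiotherapy would enter the primary safety counts. The documents do not support that. Section 12.2 bases the safety analysis on events with onset on or after the start of therapy, and section 14 assigns pre-existing conditions expected to worsen to medical history.

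**Conclusion.** The point holds as a gap in the lesion definition. Applied as written, the rule can place a previously irradiated lesion among the non-irradiated targets and count its delayed shrinkage in a listed secondary outcome and in the abscopal question. This rests on reading section 9.3 as referring to study radiotherapy, and on no unseen document supplying the missing rule.

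The size of the bias cannot be computed from the documents, and the percentages above are illustrations only. A reader might infer that one misclassified lesion is enough to create a response. It is enough only where that lesion drives the 30% fall in the sum. A reader might also see a serious contradiction in section 7, which describes patients "who are being considered for or undergoing palliative radiation therapy for pain and symptom management". Sections 8.1, 8.2 (criterion 6) and 9.2 all describe radiotherapy still to come, so this is one loose word, worth reconciling but not part of the main finding.

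**What to change.** In sections 9.3 and 10.4.8, define a non-irradiated lesion as one never irradiated, in this study or before it. Use the screening radiotherapy history to flag each previously irradiated lesion, with site and date, as a separate category. Do not select flagged lesions as non-irradiated targets, and leave them out of the abscopal summary. They can still be listed.

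Two minor clarifications belong with this: state whether criterion 11 is meant to cover prior radiotherapy, and reconcile 'undergoing' in section 7 with sections 8.1 and 9.2. Any choice of interval is a clinical matter for the sponsor.

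The cost is a sentence in each of two sections and a per-lesion entry on the case report form, drawn from history already reviewed. The small downside is that slightly fewer lesions will qualify as non-irradiated targets.

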Progressive Disease (PD):	At least a 20% increase in the sum of the LD of relevant target lesions, taking as reference the smallest sum LD recorded since the treatment started or the appearance of one or more new lesions.

Evaluation of non-target lesions

Non-measurable Assessment:

Complete Response (CR):	Disappearance of all non-target lesions and normalization of tumour marker level
--------------------------------	--

Non-CR/Non-PD:	Persistence of one or more non-target lesion(s) or/and maintenance of tumour marker level above the normal limits
Progressive Disease (PD):	Appearance of one or more new lesions and/or unequivocal progression of existing non-target lesions.

Measurable Assessment:

Response	Percent change in lesion size based on sum LD (mm) taking as reference the baseline sum LD.
-----------------	---

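### Section 10.4.8 scores target lesions by longest diameter and defines complete response as disappearance, with no rule for lymph nodes, so a normalised but visible target node cannot be CR and may score SD

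*Combined protocol and SAP*

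**What the plan says.** Section 9.3 states that lesions, whether for irradiation or not, that are at baseline "identified as measurable will be noted as target lesions and will be assessed for response to treatment according to RECIST 1.1 criteria". It refers to section 10.4.8 for further detail.

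Section 10.4.8 gives one measurement rule: "For measurable lesions, the Longest Diameter (LD) of each lesion will be measured and a sum of the LD will be calculated". That sum is the reference for response. The target-lesion categories are then written out:

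- CR: "Disappearance of all relevant target lesions".
- PR: "At least a 30% decrease in the sum of the LD of relevant target lesions, taking as reference the baseline sum LD".
- SD: "Neither sufficient shrinkage to qualify for PR nor sufficient increase to qualify for PD".
- Progressive disease (PD): "At least a 20% increase in the sum of the LD of relevant target lesions" from the smallest sum recorded, or a new lesion.

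Targets are capped at 5 in total and 2 per organ. Measurable lesions beyond the cap are non-target lesions. They are reported as percent change in summed longest diameter, with no CR category.

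Section 10.4.8 does not mention lymph nodes. Inclusion criterion 5(i) in section 8.2 does name nodal disease: "Radiographic progression of in nodal or visceral metastases". Sections 6.2, 9.3, 10.1, 10.2.14 and 12.2 all name RECIST 1.1 as the standard.

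**The concern.** A lymph node is a normal structure. When treatment succeeds, a nodal metastasis can shrink to a normal node that is still visible on the scan. A rule that requires disappearance does not recognise that outcome as complete, and the residual length limits the percent shrinkage that can be recorded.

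The categories are used in three places. They are listed as secondary outcomes for irradiated and non-irradiated targets separately (sections 6.2 and 10.1), which is where the sensitisation and abscopal questions are examined. Section 12.1 attributes to NOX66 any response beyond the reduction of less than 30% expected from palliative radiation alone. RECIST-assessed scans are also part of what the Study Steering Committee reviews at Week 6 before choosing the expansion dose (section 10.2.14).

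**Working it through.** The plan states no figure on this point, so there is none to reproduce. The check applies the section 10.4.8 categories to illustrative sizes.

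**Inputs from the documents**
- Measurement: longest diameter, summed over the relevant target lesions.
- CR: the sum is 0 (all relevant targets gone).
- PR: fall of at least 30% from the baseline sum.
- PD: rise of at least 20% from the smallest sum, or a new lesion.
- SD: anything else.

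**Assumed inputs.** All node sizes are assumptions. The documents give neither a normal node size nor a size at which a node becomes measurable.

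**Step 1: CR.** If a normalised target node keeps a visible length r > 0, the sum is at least r. CR is therefore not available while the node is visible.

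**Step 2: where SD begins for a single target node.** With baseline length B and residual r, the fall is (B − r)/B. It is under 30% when B < r/0.70.

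| Assumed normal residual r | r/0.70 | Scored SD if baseline was below |
|---|---|---|
| 10 mm | 10/0.70 | 14.3 mm |
| 12 mm | 12/0.70 | 17.1 mm |
| 15 mm | 15/0.70 | 21.4 mm |

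One-lesion sums are plausible because irradiated and non-irradiated targets are reported separately.

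**Step 3: worked cases**

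| Case | Sum, baseline to follow-up | Change | Category as written |
|---|---|---|---|
| Single node | 20 to 15 mm | −5/20 = −25% | SD |
| Single node | 25 to 18 mm | −7/25 = −28% | SD |
| Single node | 20 to 14 mm | −6/20 = −30% | PR |
| Single node | 20 to 9 mm | −11/20 = −55% | PR |
| Single node, no longer visible | 20 to 0 mm | −100% | CR |
| Node 20 to 9 mm; other targets 30 to 0 mm | 50 to 9 mm | −41/50 = −82% | PR |
| Node 20 to 9 mm; other targets 30 mm, unchanged | 50 to 39 mm | −11/50 = −22% | SD |

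The sixth row is the clearest case. All non-nodal target disease has gone and the node is down to 9 mm, yet the patient is recorded as PR. The last row is not in itself an error, because the other disease has not changed. It shows only that the summed length decides the category.

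**Step 4: effect on counts.** A CR recorded as PR changes the CR and PR listings but not the count of CR plus PR. Only a responder recorded as SD changes that count.

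**The case against.** The strongest reply is that the plan names RECIST 1.1 throughout, so trained readers will apply the guideline and treat the written table as shorthand. The sentence that introduces the table also literally covers irradiated measurable lesions; non-irradiated targets are simply assigned to RECIST 1.1. This has weight, but it does not settle the matter. That sentence says the criteria are those set out below it, and the summing rule covers all measurable lesions. At best there are two candidate rule sets for the investigator and the central review, and the recorded category could depend on which one a reader follows.

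Other objections limit the size of the point:
- The number of patients with nodal targets is unknown. Criterion 5(i) is one of two alternative routes to eligibility, and the examples given of irradiated measurable targets are soft-tissue and lytic bone lesions.
- Measurability is left to RECIST 1.1. The SD range in Step 2 may be narrow, or empty at its low end.
- The Radiation Oncology Expert Committee gives its own overall evaluation from scans, PSA, ECOG and pain (section 10.4.9). That is a separate assessment and does not repair the RECIST categories.

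A reader might infer four stronger things that the documents do not support:
- *Nodal disease can never be CR.* A target node that is no longer visible is CR as written.
- *The rule covers every measurable lesion.* Targets are capped, and measurable non-target lesions have no CR category.
- *One patient in a cohort of 4 moves a response rate by 1/4 = 25 percentage points.* This needs a responder recorded as SD and all four patients evaluable. The plan sets no cohort response-rate threshold, and the synopsis lists outcomes per patient.
- *The dose choice is biased.* The Week 6 decision is a committee judgement on safety, disease status, scans and pain, with no response cut-off. The same rule applies at every dose.

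**Conclusion.** The point holds for target lesions. The criteria written in section 10.4.8 give no way to record a normalised but visible target node as a complete response. Such a patient scores PR, or SD if the sum falls by less than 30%. That lymph nodes fall under the rule follows from the absence of an exception, since the section does not mention them.

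The size is modest and partly unknown. The limits of 14.3, 17.1 and 21.4 mm rest on assumed normal residuals of 10, 12 and 15 mm and on a single nodal target, and the documents do not say whether nodes that small would be measurable. The problem can shift the CR, PR and SD listings, the reduction beyond 30% that section 12.1 attributes to NOX66, and the scan data seen at the Week 6 review. The outcome is secondary and descriptive, so no error rate or sample size is affected. It should be corrected, because the plan's written criteria decide a category that the cited standard is meant to decide.

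**What to change.** Before data lock, in section 10.4.8 and in the detailed SAP that section 12.2 announces:

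1. For nodal target lesions, replace the longest-diameter and disappearance wording with the nodal measurement axis and CR cut-off of the RECIST 1.1 guideline already cited (reference 40). Both should be copied from that source, since the plan states neither. Keep longest diameter for non-nodal targets.
2. Define CR as disappearance of all non-nodal targets together with return of all nodal targets to normal size by that cut-off.
3. In the PR, SD and PD rows, refer to the sum of diameters instead of the sum of longest diameters.
4. State that the rule applies to irradiated and non-irradiated targets alike, and to both investigator and central assessments.
5. Re-measure nodal targets on the stored scans from baseline and Weeks 6, 12 and 24 (section 9.3). State how a node is handled if it was chosen on longest diameter but does not qualify under the guideline's nodal rule.

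The cost is a wording change and a small amount of re-measurement. No new imaging and no additional patients are needed.
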